6.4.2 Study Drug Overdose

Study drug overdose is the accidental or intentional use of the drug in an amount higher than the dose being studied. Any study drug overdose or incorrect administration of study drug should be noted on the appropriate CRF. Any accidental or intentional overdose with the study treatment, even if not fulfilling a seriousness criterion, is to be reported to the sponsor-investigator within 1 business day, to TG Therapeutics, Inc. at [contact] within 24 hours, and to Acerta Pharma at [contact] within 15 calendar days on an SAE form (CIOMS, local institutional SAE form, or similar).

6.4.3 Secondary and Second Primary Malignancy

Secondary and second primary malignancies are considered AESIs for acalabrutinib. Any malignancy possibly related to cancer treatment, and any secondary (occurring as a direct result as study drug administered, including but not limited to MDS) or second primary (unrelated, new cancer, including but not limited to MDS and MPD) malignancy event must be reported to the sponsor-investigator and to Acerta Pharma at: [contact] via the SAE form (CIOMS, local institutional SAE form, or similar) within 1 business day of awareness.

AEs for malignant tumors reported during a study should generally be assessed as serious AEs (refer to **Section 7.3**). If no other seriousness criteria apply, the “considered significant by the investigator for any other reason” criterion should be used. In certain situations, however, medical judgement on an individual event basis should be applied to clarify that the malignant tumor event should be assessed and reported as a Non-Serious AE. For example, if the tumor is included as medical history and progression occurs during the study, but the progression does not change treatment and/or prognosis of the malignant tumor, the AE may not fulfill the attributes for being assessed as serious, although reporting of the progression of the malignant tumor as an AE is valid and should occur. Also, some types of malignant tumors, which do not spread remotely after a routine treatment that does not require hospitalization, may be assessed as Non-Serious; examples include Stage 1 basal cell carcinoma and Stage 1A1 cervical cancer removed via cone biopsy.

6.4.4 Ventricular Arrhythmias

Ventricular arrhythmias (e.g. ventricular extrasystoles, ventricular tachycardia, ventricular arrhythmia, ventricular fibrillation, etc.) are considered AESIs for acalabrutinib. Any occurrence of a ventricular arrhythmia must be reported to the sponsor-investigator and Acerta Pharma irrespective of regulatory seriousness criteria or event causality. Report on an SAE form (CIOMS, local institutional SAE form, or similar) within 15 calendar days of awareness, email form to Acerta Pharma at: [contact]

6.5 Adverse Event Reporting

- 6.5.1 In the event of an unanticipated problem or life-threatening complications treating investigators must immediately notify the PI.
- 6.5.2 Investigators **must** report to the PI any serious adverse event (SAE) or adverse event of special interest (AESI) that occurs after the initial dose of study treatment, during treatment, or within 30 days of the last dose of treatment on the local institutional SAE form.

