Furthermore, recent *in-vitro* data suggests that acalabrutinib, as opposed to ibrutinib, has favorable activity against CLL cells together with CD20 antibodies, and does not mitigate ADCC, likely because it is a much more specific inhibitor of BTK.²³ A later antibody administration, when disease is already reduced, is also employed here, as it should lead to more favorable antibody pharmacokinetics and perhaps better clearance of residual disease. This hypothesis has some support from an ASH abstract presented in 2018, which suggested that delayed administration of obinutuzumab with ibrutinib resulted in a significantly higher CR rate than early obinutuzumab administration.²⁴

We therefore plan to build on the prior phase 1 experience with ibrutinib-umbralisib and ibrutinib, umbralisib, ublituximab, by substituting acalabrutinib in a phase 2 study of the three-drug combination. From data available from separate clinical studies, acalabrutinib appears to be better tolerated than ibrutinib so this should not cause any unexpected toxicity. This study targeting less heavily pretreated patients will better establish the efficacy of the combination as measured by CR rate and PFS in untreated CLL patients and early relapsed patients.

The trial will have another two novel therapeutic approaches. First, ublituximab administration will be delayed in an attempt to improve its ability to clear residual bone marrow disease at a point when significant cytoreduction has already occurred and the half-life of the antibody should be prolonged. Second, treatment will be given for only 12 – 24 cycles, thus mitigating long-term adverse events and potentially reducing selection pressure for resistant clones. Patients who are not heavily pre-treated, especially those who are treatment-naïve, may benefit from a long drug-free period before they progress, at which time they could theoretically receive the same regimen again.

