4.6 Duration of Follow Up

Participants will be followed for 30 days after removal from protocol therapy or until death, whichever occurs first, for adverse events. Participants removed from protocol therapy for unacceptable adverse event(s) will be followed until resolution or stabilization of the adverse event. Following the 30 day follow up period, participants will be followed for a maximum of 5 years after treatment discontinuation to observe treatment response and survival status.

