6.3 Serious Adverse Event Reporting

A serious adverse event (SAE) is any adverse event that occurs after the initial dose of study treatment, during treatment, or within 30 days of the last dose of treatment that results in one of the following outcomes or meets at least one of the following criteria:

- Death
- Hospitalization for greater than 24 hours
- Prolonging an existing inpatient hospitalization
- A life-threatening experience (that is, immediate risk of dying)
- Persistent or significant disability/incapacity
- Congenital anomaly/birth defect
- Any suspected transmission of an infectious agent via a study agent (e.g. Prion Protein Transmitting Transmissible Spongiform Encephalopathy)
- Any confirmed occurrence of Hy's Law, defined as an ALT or AST $\geq 3 \times$ institutional ULN **AND** concurrent total bilirubin $\geq 2 \times$ institutional ULN without findings of cholestasis
- Considered significant by the investigator for any other reason

If an investigator becomes aware of an SAE that is considered related to acalabrutinib after completion of the 30-day period following the last dose of acalabrutinib, the event should also be reported as an SAE to Acerta Pharma at the contact information given below.

Previously planned (prior to signing the informed consent form) surgeries, and non-disease related elective surgeries planned during the course of the study, should not be reported as SAEs unless the underlying medical condition has worsened or appeared during the course of the study. Events that occur prior to the first administration of study medication should not be reported as SAEs.

Preplanned hospitalizations or procedures for pre-existing conditions that are already recorded in the patient's medical history at the time of study enrollment should not be considered SAEs. Hospitalization or prolongation of hospitalization without a precipitating clinical AE (e.g., for the administration of study therapy or other protocol-required procedure) should not be considered SAEs.

Important medical events that may not result in death, be life-threatening, or require hospitalization may be considered SAEs when, based on appropriate medical judgment, they may jeopardize the patient and may require medical or surgical intervention to prevent one of the outcomes listed in this definition.

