Acalabrutinib ^m		As described in Section 5.3												Day 1 of Cycles 1 - 12
Umbralisib ^m		As described in Section 5.3												Day 1 of Cycles 1 - 12
Medical Record Review / Care Provider Contact / Telephone Contact												X		Every 3 months following treatment discontinuation for a maximum of 5 years

^{oo}: Column only relevant for CRF builders.

- a. A \pm 3 day scheduling window is allowable to account for holidays, adverse weather, vacations, or any other scheduling issues.
- b. A \pm 7 day scheduling window is allowable to account for holidays, adverse weather, vacations, or any other scheduling issues.
- c. A \pm 2 day scheduling window is allowable to account for holidays, adverse weather, vacations, or any other scheduling issues.
- d. Off treatment evaluation. Note: for IND trials, follow up visits or other contact are required in order to identify SAEs during the 30 days following the end of study treatment.
- e. Long-term follow-up will involve medical record review, telephone and/or care provider contact to confirm survival status and ongoing disease response following treatment discontinuation. To be completed every 3 months following the final dose of study drug (\pm 1 month window) for a maximum of 5 years after treatment discontinuation or until death, whichever occurs first.
- f. Albumin, alkaline phosphatase, total bilirubin, bicarbonate, BUN, calcium, chloride, creatinine, glucose, potassium, total protein, SGOT [AST], SGPT [ALT], sodium, phosphorus, uric acid, LDH.
- g. Serum pregnancy test within 3 days prior to Cycle 1 Day 1 only required for women of childbearing potential, as defined in **Section 5.4**.
- h. Hepatitis B surface antigen (HBsAg) and antibody (HBsAb), hepatitis B core antibody (HBcAb), HBV DNA, hepatitis C antibody, hep C viral load and CMV IgG or IgM testing is required for all participants during the screening period. Refer to **Section 3.2.20** and **Section 5.4**.
- i. Single EKG to be collected during the screening period. QTc to be calculated per institutional standards.
- j. Screening chest/abdomen/pelvis CT or MRI required for all participants within 30 days prior to the start of protocol therapy. Refer to **Section 11.1**.

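### Second-malignancy reporting has no end date in section 6.4.3 but stops 30 days after the last dose in sections 6.5.2 and 4.6, and the long-term contacts name neither second cancers nor the start of next therapy

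*Combined protocol and SAP*

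**What the plan says.** Second cancers are a named key risk of acalabrutinib (section 2.4.1.4) and carry special status in section 6.4.3: "Secondary and second primary malignancies are considered AESIs for acalabrutinib". That section says any such "malignancy event must be reported to the sponsor-investigator and to Acerta Pharma at" a given address, "within 1 business day of awareness". It sets no closing date.

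Section 6.5.2 requires investigators to report serious adverse events and adverse events of special interest to the principal investigator, and limits the duty to an event (the second class abbreviated there as AESI) in these terms: "AESI) that occurs after the initial dose of study treatment, during treatment, or within 30 days of the last dose of treatment". Section 4.6 follows adverse events for 30 days after removal from protocol therapy. The exception is a participant removed for an unacceptable event, who is followed until that event resolves or stabilises. After that, "participants will be followed for a maximum of 5 years after treatment discontinuation to observe treatment response and survival status".

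The 3-monthly contact is described in the footnotes to Tables 20 to 23: "Long-term follow-up will involve medical record review, telephone and/or care provider contact to confirm survival status and ongoing disease response". Tables 20, 22 and 23 run it for up to 5 years after treatment discontinuation. Table 21, for participants in CR, runs it for up to 2 years after Cycle 36. Table 21 also keeps an adverse-event evaluation row at the off-drug visits from Cycle 13 to Cycle 37.

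Section 10.4 defines TTNT by the start of an alternative therapy for progressive CLL. Sections 1.3 and 12.5 ask for its 2-, 3- and 5-year rates.

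**The concern.** Second cancers tend to appear late, and the plan's case for stopping treatment rests partly on late safety: "treatment will be given for only 12 – 24 cycles, thus mitigating long-term adverse events". A site reading section 6.4.3 would report a cancer found in year 3. A site reading sections 6.5.2 and 4.6 could conclude that reporting closed at day 30. With both readings open, counts depend on the site.

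Even under the broader reading, the duty begins only when someone becomes aware of the cancer, and no listed item of the long-term contact asks about it. At stake is a descriptive safety result that is incomplete and covers different lengths of time for participants who stop in CR and those who complete 24 cycles. The same contacts are the main source of late TTNT dates, and they do not name the date that the endpoint requires.

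**Working it through.** **The reporting rules side by side**

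- Section 6.4.3: triggered by awareness; goes to the sponsor-investigator and the acalabrutinib supplier; no end date.
- Section 6.5.2: goes to the principal investigator; ends 30 days after the last dose.
- Section 6.3: the serious adverse event definition, to which section 6.4.3 refers malignancies, ends at 30 days. A later event is covered only if considered "related to acalabrutinib after completion of the 30-day period following the last dose of acalabrutinib", and that report goes to the supplier. Section 6.4.3 describes a second primary as a new, unrelated cancer, so this rule need not reach it.
- Section 4.6: 30 days for adverse events, then response and survival only.

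**The plan's own figure**

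Section 12.2 states about 8 years in total. With 15 months of accrual, 24 cycles of 28 days and 5 years of follow-up: 15/12 + (24 × 28)/365.25 + 5 = 1.25 + 1.84 + 5 = 8.09 years. This agrees, and it uses 5 years of follow-up, as section 4.6 does, rather than Table 21's 2 years.

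**Length of scheduled adverse-event evaluation, from first dose**

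- CR at Cycle 12, followed under Table 21 to Cycle 37 Day 1: 36 × 28 = 1008 days.
- 24-cycle completers: 24 × 28 + 30 = 702 days.
- Ratio: 1008/702 = 1.4.

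**Follow-up time with no scheduled adverse-event question**

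After Cycle 37 a CR participant has up to 2 years of contacts. A 24-cycle completer has 5 − 30/365.25 = 4.92 years. Assuming no deaths or losses among 60 participants:

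| Participants stopping in CR | Person-years | Events at 1 to 2 per 100 person-years (assumed) |
|---|---|---|
| All 60 | 60 × 2 = 120 | 1.2 to 2.4 |
| 28 | 28 × 2 + 32 × 4.92 = 213 | 2.1 to 4.3 |
| None | 60 × 4.92 = 295, at most 60 × 5 = 300 | about 3 to 6 |

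The middle row applies the hypothesised CR rates of section 12.4 (0.44 × 30 + 0.50 × 30 = 28.2) as if already reached at Cycle 12, which is an assumption.

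**TTNT and the 5-year landmarks**

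- Last scheduled visit for 24-cycle completers, Cycle 25 Day 1: 672/365.25 = 1.84 years from first dose.
- Last scheduled visit for CR participants, Cycle 37 Day 1: 1008/365.25 = 2.76 years.
- Unless a participant is re-treated, next-therapy dates after these points depend on the long-term contacts. That covers the 3- and 5-year rates.
- End of contacts under Table 21: 2.76 + 2 = 4.76 years, or 4.84 with the one-month window. Both fall short of 5 years.
- End of contacts for the same participant under section 4.6: (12 × 28)/365.25 + 5 = 5.92 years.
- End of contacts for 24-cycle completers: 1.84 + 5 = 6.84 years.

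Under Table 21, every event-free CR participant who is not re-treated is therefore censored before the 5-year landmark. The last part of the Kaplan-Meier curve would then rest on the other participants.

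**The case against.** The strongest reply is that section 6.4.3 is a specific rule for exactly these events, and a general rule such as section 6.5.2 does not cancel it. Participants stay on study until the 5-year follow-up ends (section 4.7). Medical record review and care-provider contact every 3 months could plausibly reveal a new cancer or a new CLL therapy, and a cancer would then trigger section 6.4.3. The case report forms are not in the documents. No endpoint is second-malignancy incidence, and no comparison of 12-cycle with 24-cycle participants is planned.

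Much of this stands, and it rules out several stronger readings that a reader might infer:

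- That malignancies are reportable only up to day 30. Section 6.4.3 and the late-event rule in section 6.3 contradict this.
- That adverse-event evaluation differs about 22-fold between the groups (672 versus 30 days after the last dose). This ignores time on treatment. From first dose the ratio is 1.4.
- That 300 person-years is the expected gap. It is the ceiling, reached only if nobody stops in CR, dies or is lost.
- That no form collects these items. This cannot be shown without the forms.

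The reply does not remove the conflict between sections, and it leaves late capture dependent on awareness rather than on a specified question.

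**Conclusion.** The point holds as a gap in what the protocol specifies. Section 6.4.3 conflicts with sections 6.5.2 and 4.6 on how long second malignancies are reportable. After the scheduled visits their capture is passive, and the contact footnotes do not name the next-therapy start date.

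The size is modest: about 120 to 300 person-years without a scheduled question, or about 1 to 6 events. The event rate is an assumption that the documents do not supply, and deaths or losses would lower both ends of the range. In 60 participants even a few missed cancers would alter a descriptive safety summary.

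The difference between Table 21 and section 4.6 in contact length is a second inconsistency, and it bears directly on the 5-year TTNT, progression-free survival and overall survival rates. The primary endpoint, sample size and error rates are unaffected. The change should be made, but the design does not depend on it.

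**What to change.** - State in sections 6.5.2 and 4.6 that malignancies covered by section 6.4.3 are reportable until the end of study follow-up.
- Add two items to the long-term follow-up footnotes of Tables 20 to 23: second malignancy (date, type) and next CLL therapy (start date, name).
- State in section 12.5 that second malignancies will be reported from first dose to last contact, with person-time, in all treated participants.
- Reconcile the Table 21 contact length (2 years after Cycle 36) with section 4.6 (5 years after treatment discontinuation), so that follow-up of CR participants reaches the 5-year landmarks.

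The cost is a few sentences of protocol text and slightly more data entry at contacts that already take place every 3 months. No visits are added. If the longer contact period is adopted for CR participants, their existing type of contact continues for about 5.92 − 4.76 = 1.16 more years.

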6.5.3 DF/HCC Adverse Event Reporting Guidelines

Investigative sites within DF/HCC will report AEs directly to the DFCI Office for Human Research Studies (OHRS) per the DFCI IRB reporting policy.

Other investigative sites will report AEs to their respective IRB according to the local IRB's policies and procedures in reporting adverse events. A copy of the submitted institutional AE form should be forwarded to the Sponsor-Investigator within the timeframes detailed below:

- **Grade 2 and Grade 3 Events:** Report events that are unexpected and there is a reasonable possibility the event is related to the study intervention (i.e. possible, probable, or definite attribution). Report to the sponsor-investigator within 5 calendar days of the treating investigator or research site personnel learning of the event.
- **Grade 4 Events:** Report all events that are unexpected. Report to the sponsor-investigator within 5 calendar days of the treating investigator or research site personnel learning of the event.
- **Grade 5 Events:** Report ALL grade 5 events. Report to the sponsor-investigator within 1 business day of the treating investigator or research site personnel learning of the event.

The Sponsor-Investigator will submit AE reports from outside institutions to the DFCI OHRS according to DFCI IRB policies and procedures in reporting adverse events.

6.6 Reporting to the Food and Drug Administration (FDA)

The Sponsor-Investigator will be responsible for all communications with the FDA. The Sponsor-Investigator will report to the FDA, regardless of the site of occurrence, any serious adverse event that meets the FDA's criteria for expedited reporting following the reporting requirements and timelines set by the FDA.

Any adverse events meeting criteria for FDA reporting must also be reported to Acerta Pharma in parallel with FDA submission: [contact].

6.7 Reporting to Hospital Risk Management

Participating investigators will report to their local Risk Management office any participant safety reports, sentinel events or unanticipated problems that require reporting per institutional policy.

6.8 Routine Adverse Event Reporting

All Adverse Events **must** be reported in routine study data submissions to the PI on the toxicity case report forms. **AEs reported through expedited processes (e.g., reported to the IRB, FDA,**

etc.) must also be reported in routine study data submissions.

7. PHARMACEUTICAL INFORMATION

A list of the adverse events and potential risks associated with the investigational agents administered in this study can be found in **Section 7.1**.

7.1 Acalabrutinib maleate

7.1.1 Description

Other Names: CALQUENCE®, ACP-196 Maleate
Molecular Formula: $C_{26}H_{23}N_7O_2.C_4H_4O_4$
Molecular Weight: 581.58
Appearance: Orange film-coated tablet

7.1.2 Form

The investigational product, acalabrutinib maleate tablet, is presented as an orange film-coated tablet containing 129 mg of acalabrutinib maleate (equivalent to 100 mg of acalabrutinib) drug substance.

Each tablet also contains the following compendial inactive ingredients: mannitol, microcrystalline cellulose, low-substituted hydroxypropyl cellulose and sodium stearyl fumarate. The tablet coating contains: hypromellose, copovidone, titanium dioxide, polyethylene glycol, caprylic/capric triglyceride, yellow iron oxide and red iron oxide.

7.1.3 Storage

Acalabrutinib maleate tablets are packed in white, high-density polyethylene (HDPE) bottles containing a silica gel desiccant and should be stored according to the storage conditions as indicated on the label. The recommended storage condition for acalabrutinib maleate tablets is below 30°C (86°F)

7.1.4 Handling

Qualified personnel, familiar with procedures that minimize undue exposure to themselves and the environment, should undertake the preparation, handling, and safe disposal of the chemotherapeutic agent in a self-contained and protective environment.

7.1.5 Availability

Acalabrutinib is a commercially available agent that will be supplied by Acerta Pharma.

7.1.6 Administration

See **Section 5.3.**

7.1.7 Ordering

Acalabrutinib should be ordered from Acerta Pharma by site pharmacy personnel.

7.1.8 Accountability

The investigator, or a responsible party designated by the investigator, should maintain a careful record of the inventory and disposition of the agent using the NCI Drug Accountability Record Form (DARF) or another comparable drug accountability form. (See the NCI Investigator's Handbook for Procedures for Drug Accountability and Storage.)

7.1.9 Destruction and Return

Expired, returned, or unused supplies of acalabrutinib should be destroyed according to local institutional policies. Destruction will be documented in the Drug Accountability Record Form.

